6.6 Complications and Review Form

This form is to be used to record all complications that occur in a patient throughout the entire time that the patient is in the study. There is only one form per patient (the form does not repeat). It can be used for complications that are caught during a follow-up Saturday clinic or when a patient reports a complication outside of a clinic.

1. Notes on how to use this form

- a. The most important thing is to never uncheck an Event # checkbox that already has information stored in it. If this is done, a warning message will appear asking you if you want to delete the information or note. Press "OK" if your intention is to delete the information. If it was an accident, press "CANCEL" and then check the box that you accidentally unchecked. If any information is lost, leave the form and press "Leave and do not save record" when the warning message appears. If any information was accidentally deleted, please tell [name]. He may have a backup of the data if the data was not reported very recently. If he does not have a backup, he may be able to contact REDCAP or UCSF to retrieve the data.

2. Overview

- a. Whenever a new complication needs to be reported, check the appropriate checkbox in order to open the questions where information can be recorded. It is important to note that Event #2 does not refer to "report two events", it refers to "report the second event".

b. Delayed exfix removal has its own types of questions and is listed separately. This is only for patients on exfix who need to stay on the exfix longer than 3 months.

Overview of Complications		
Has the patient died?	 Yes	reset
Which MEDICAL complication do you want to report?	 Event #1  Event #2  Additional Events	
Which SURGICAL complication event do you want to report? (Do not uncheck boxes of events that have already been reported)	 Event #1  Event #2  Event #3  Additional Events  Delayed Exfix Removal	

3. Mortality
 - a. To be used only if the patient has died
 - b. A query needs to be opened (See “Adjudication Review” Section)
4. Medical Complications
 - a. The most important thing to record for medical complications is whether or not the patient needed to be hospitalized.
 - b. Medical complications do not be reported unless there is concern that needs to be reviewed by the review committee
 - c. Any additional medical problems beyond 2 events need to be reported in free text entry in a text box. Number the medical complication events accordingly (Event #3...)

Medical Event #1

What day was the medical problem first diagnosed by the physician?

 Today D-M-Y

Format is DD-MM-YYYY. Insert date manually, by clicking on the calendar image above, or press "Today" if applicable

What kind of medical problem does this patient have?

* must provide value

- Stroke/Hemorrhage
- Heart Attack
- Pulmonary Embolism
- Pneumonia
- Deep Vein Thrombosis (DVT)
- Allergic Reaction
- Other/Multiple

[reset](#)

Describe the medical problem here

[Expand](#)

What kind of treatment did the patient receive?

- Treatment with hospitalization
- Treatment without hospitalization
- No Treatment

[reset](#)

Describe the treatment

[Expand](#)

Where was the patient hospitalized?

How many days was the patient hospitalized for?

Additional Medical Problems

Describe details of all other medical problems including:

- 1, Date of diagnosis
- 2, Type of problem
- 3, Treatment
- 4, Number of days hospitalized (if applicable)
- 5, Location of hospitalization (if applicable)

[Expand](#)

5. Surgical Complications

- a. If a surgical complication requires reoperation, record the estimated date and press "No" if the reoperation has not occurred yet. Patients who are awaiting reoperation will appear on the "Awaiting Reoperation" report.
 - i. Record "no" for the question "has this been reviewed yet". This will cause the complication to appear on the "Adjudication Review" report. Once the item

has been reviewed, [name] will record "yes" which will remove the complication from the report.

b. Once the patient has had their reoperation, change the answer to "Yes" and record the actual date of the reoperation.

Surgical Complication #1	
What day was the complication first diagnosed by a physician?	   Format is DD-MM-YYYY. Insert date manually, by clicking on the calendar image above, or press "Today" if applicable
What is the surgical complication? <small>* must provide value</small>	 Superficial Surgical Site Infection  Deep Surgical Site Infection  Delayed Wound Healing  Nonunion/Delayed Union  Malignancy/Malunion  Hardware Failure (Non-infectious)  Missed Interlock  Compartment Syndrome  Other/Multiple 
Describe the details of the complication <small>* must provide value</small>	 
Upload any relevant images here (if available):	Upload document
Is reoperation being considered for this complication? <small>* must provide value</small>	 Yes  No 
Which hospital will the reoperation be performed at?	
ESTIMATED date of reoperation	   Format is DD-MM-YYYY. Insert date manually, by clicking on the calendar image above, or press "Today" if applicable

Has the reoperation been performed?

* must provide value

No
 Yes
 The patient no longer needs a reoperation

reset

This patient will now appear on the "Awaiting Reoperations" report. After the reoperation, change the answer to the above question to "Yes"

ACTUAL date of reoperation

Describe the reoperation that was performed:

Complication #1 Review

Has this issue been reviewed?

* must provide value

Yes
 No

reset

This issue needs to be reviewed.

Date of Review

Format is DD-MM-YYYY. Insert date manually, by clicking on the calendar image above, or press "Today" if applicable

Results of Review

* must provide value

- c. Additional surgical complications beyond the third event should be recorded in free text entry box. Label the event # accordingly (Event #4...)

Additional Surgical Complications

If the patient has had more than 3 surgical complications, describe them here. Include the following information:

1. Date complication first diagnosed by physician
2. Details of complication

If reoperation is being considered:

3. Type of surgery planned
4. Hospital
5. Estimated date of reoperation
6. Actual date of reoperation

[Expand](#)

Is reoperation being considered for any of these complications?

Yes
 No

* must provide value

[reset](#)

Please send [name] an email and he will manage the review of these reoperations.

[name]'s email: [contact]

Have all reoperations been performed?

No
 Yes
 The patient no longer needs a reoperation

* must provide value

[reset](#)

This patient will now appear on the "Awaiting Reoperations" report. After the reoperation, change the answer to the above question to "Yes"

6. Delayed exfix removal

- a. For patients who need to stay on exfix for longer

Delayed Exfix Removal (Exfix Patients Only)

Describe the reason for delayed exfix removal

[Expand](#)

Has the exfix been removed yet?

* must provide value

Yes
 No

[reset](#)

This patient will now appear on the "Delayed Exfix" report. After the reoperation, change the answer to the above question to "Yes"

What day was the exfix removed?

[Today](#) [D-M-Y](#)

Format is DD-MM-YYYY. Insert date manually, by clicking on the calendar image above, or press "Today" if applicable

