The proposed study will be a prospective, randomized trial conducted at Muhimbili Orthopaedic Institute (MOI) in Dar es Salaam, Tanzania. All skeletally mature patients presenting to the emergency department between December 2015 and December 2016 meeting inclusion criteria will be consented and enrolled in the study. Baseline clinical data will be obtained during enrollment. The patients will then undergo a standard wound debridement protocol (regardless of treatment arm) followed by intraoperative confirmation that the wound can be primarily closed. If so, the patient will be randomized using the REDCAP randomization module to one of two treatment arms: intramedullary nailing or external fixation. Primary and secondary outcomes will be measured prospectively during the postoperative period and at subsequent follow-up visits at 2wk, 6wk, 3mo, 6mo, and 1yr (Sections 2.6 and 2.7). Serious adverse events that occur during the study will be presented to all co-investigators (Section 3.2). Interim analysis will be produced and reviewed by all co-investigators every 6 months, with a final report generated within three months of the trials end (Section 2.9 and 3.3).

UCSF-MOI Open Tibia Study Overview

[figure not shown]

Figure 1: Timeline for patient enrollment and data collection

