5.8 Follow-up Schedule

Participants will be scheduled for follow up appointments at 2 weeks, 6 weeks, 3 months, 6 months, and 1 year after the date of surgery. The 2 week visit is primarily a wound check to assess the wound and record any other surgical or medical complications that may have arisen since discharge. The remaining follow up appointments will include clinical evaluation, plain radiographs (AP and lateral views), and administration of the EQ-5D. The follow up schedule will be generated using the scheduling function in REDCap. All research clinic appointments will be conducted in a dedicated research clinic on Saturday afternoons. Every research clinic will be staffed by one of the study investigators ([name]), at least one research coordinator, and a research nurse.

Because the follow-up clinics occur on Saturdays, the following rounding system will be used to calculate which date the patient should come for a follow up visit:

- For patients that get operated on a Sunday, Monday, or Tuesday, the previous Saturday will be used to calculate the 2 week follow up date (and all other subsequent dates)
- For patients that get operated on a Wednesday, Thursday, Friday, or Saturday, the upcoming Saturday will be used to calculate the 2 week follow-up date (and all other subsequent dates)

Promoting Follow Up

The following strategies will be implemented in order to improve the rate of follow up:

1. Treating patients with a high level of hospital which involves:
 - a. Introducing the study participant to all members of the team
 - b. Advocating for timely and appropriate care of the patient
 - c. Clearly informing the patient about the steps of the study
 - d. Explaining the study to the contacts that the patient provided

- e. Protecting patient confidentiality
- 2. Calling the 3 contacts that the patient provides at the time of enrollment and notifying them of the patients illness, their participation in the study, and the importance of helping them attend all follow-up visits.
- 3. Costs of follow up care will be free to study participants, including the consultation fees and cost of plain x-rays.
- 4. Saturday clinic will be separate from the general clinic and conducted in private clinic offices. This will make it easier for patients to come back to MOI, minimize waiting times, and ensure patients are able to see a specialist rather than physician in training.

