Is the patient able to perform the walking speed test? 
reset
 
  Yes  No 
		
Walking Speed Test #1 (Seconds): 
Time to walk 4 meters (in seconds)
		
Walking Speed Test #2 (Seconds): 
Time to walk 4 meters (in seconds)
		
Averaged walking speed test time 
View equation
		

5. Complications

- a. Properly recording complications is critical for the study because our end goal is to compare complication and reoperation rates between the two groups.
- b. Exfix patients will have additional questions appear related to schanz pin tract infections

Exfix Questions

Has the patient been performing proper pin-care with spirit 2x a day?

Yes
 No

reset

Please inform the patient about the importance of proper pin care

What is the plan for the exfix?

(Removal at 3 months with or without cast applied is standard procedure)

Exfix removal at 3 months
 Exfix removal AND a cast will be applied
 Delayed exfix removal
 Other (early removal, conversion, etc.)

reset

This exfix plan is not standard. Please report this as a complication in the "Complications and Review" Form

Are the Schanz pin tracts infected?

Yes
 No
 N/A (Exfix already removed)

reset

How many pins are infected?

1 2 3 4

reset

Pin tract infection level (and corresponding treatment plan):

0 - Normal (requires weekly pin care)
 1 - Inflamed (requires daily pin care)
 2 - Serous discharge (requires antibiotics)
 3 - Purulent discharge (requires antibiotics)
 4 - Osteolysis (requires removal of pin)
 5 - Ring Sequestrum (requires debridement)

reset

Since surgery is required to fix the schanz pin infection, please record the details on the "Complications" Form

- c. If the patient has a medical or surgical complication, record "Yes" and proceed to the "Complications and Review" form. That is where additional information will be recorded.
 - i. A pop-up warning will appear if a patient has had a complication recorded and is coming back for follow-up. This is to enable us to be up to date with complications.

Complications

Does the patient have any complications? These can include:

- Infection
- Wound problems
- Nonunion/malunion
- Hardware failure
- Medical problems

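### Section 6.6 item 4b, read literally, tells staff not to report medical complications unless there is a concern, against three instructions to record them; it should be reworded

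*Protocol*

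**What the plan says.** Section 6.6 of the protocol governs the Complications and Review Form. Its opening sentence sets no restriction on the kind of complication: "This form is to be used to record all complications that occur in a patient throughout the entire time". Item 2a explains how an event is entered: "Whenever a new complication needs to be reported, check the appropriate checkbox in order to open the questions where information can be recorded". Under the heading for medical complications, item 4a names hospitalization as the most important thing to record. Item 4b then says: "Medical complications do not be reported unless there is concern that needs to be reviewed by the review committee". Item 4c continues: "Any additional medical problems beyond 2 events need to be reported in free text entry in a text box".

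Two other sections deal with the same events:

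- Section 6.5, item 5c, on the follow-up evaluation form: "If the patient has a medical or surgical complication, record" a yes, and go on to the Complications and Review Form. Item 5a gives the reason: "Properly recording complications is critical for the study because our end goal is to compare complication and reoperation rates between the two groups".
- Section 5.8, on the 2-week visit, which is a wound check and is also there to "record any other surgical or medical complications that may have arisen since discharge".

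Section 4 (Methods) adds a statement on serious events: "Serious adverse events that occur during the study will be presented to all co-investigators".

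**The concern.** Item 4b stands among the working instructions that coordinators follow when they fill in the form. As printed, it puts a filter between a medical event and the database: the event is not reported unless someone thinks the committee needs to look at it. The protocol does not say what counts as a concern or who decides.

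The block concerned covers stroke or hemorrhage, heart attack, pulmonary embolism, pneumonia, deep vein thrombosis, allergic reaction and an open category. It holds the date of diagnosis, the type of event, the treatment and the details of any hospital stay. Staff at follow-up can see whether the patient has a nail or an external fixator, and the follow-up form asks extra questions of external fixator patients. A filter that rests on judgement could therefore work differently in the two arms. A comparison of medical complications would then partly reflect what was entered, not only what happened.

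The change summary at the front of the protocol shows that the wording of forms has mattered in this trial. The entry for April 2016 reports under-recording of pin tract infections among the first 40 patients. The team thought an ambiguous question may have been the cause, and changed the form.

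**Working it through.** No arithmetic applies. The check is to set the instructions side by side and ask whether they can all be followed at once.

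**1. What each instruction requires for a non-fatal medical complication that nobody regards as a concern**

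| Place | Requirement | Condition |
|---|---|---|
| 6.6, opening | Record it on this form | None |
| 6.5, item 5c | Mark yes, go to this form | None |
| 5.8, 2-week visit | Record it | None |
| 6.6, item 4c | Report it, in free text, if beyond the second event | None |
| 6.6, item 4b | Do not report it | Lifted only by a concern for the committee |

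The first three rows and the last cannot all be followed. Item 4c, directly below 4b, also fits poorly with it.

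**2. What reporting means in Section 6.6.** The conflict depends on whether reporting means entering data or referring to the committee. Item 2a uses the word for ticking a box so that the data fields open. The overview field of the form asks which medical complication the user wants to report. Item 4c uses the word for free-text entry. In each case, to report is to enter data. On the section's own usage, 4b restricts entry.

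**3. Whether repairing the grammar removes the conflict.** At least one word seems to be missing. If 4b was meant to say that medical complications need not be reported, the ban becomes a waiver. A waiver still conflicts with three unconditional instructions as long as reporting means entering data. The conflict goes away only if reporting means referral to the committee, and 4b does not say that.

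**4. What would still be captured if 4b were followed literally.** The follow-up form has one required yes/no question on complications, and medical problems are among its examples. It would show that some complication occurred. It covers infection, wound, union, hardware and medical problems together, so a yes alone does not identify a medical event. The structured details are held in the block that 4b restricts.

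**5. Which outcomes depend on that block.** The primary outcome in Section 4.1 is reoperation. The secondary clinical outcomes there are compartment syndrome, superficial and deep infection, clinical and radiographic union, malunion and implant failure. The functional outcomes are EQ-5D, pain, range of motion and functional tests. None uses the medical-event block; compartment syndrome and surgical site infection are on the surgical list. Death has its own field and goes to adjudication. What remains exposed is non-fatal medical events.

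**6. Size.** The protocol gives no rate of medical complications. The loss could lie anywhere between none, if every event is entered regardless of 4b, and all non-fatal medical events that the recorder does not see as a concern.

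**The case against.** The strongest defence is that 4b is about routing and not about data entry. Its condition refers to the review committee. The neighbouring instructions also deal with routing: item 3b has a query opened for a death, and item 5a says how a surgical event reaches the adjudication report. The list of events for review in Section 5.10 contains deaths, delayed external fixator removal and surgical complications requiring reoperation, but no medical events. The surgical block ends with review fields, and the medical block has none. On this reading, 4b says only that routine medical events need not go to the committee, and nothing conflicts. The form also offers treatment without hospitalization and no treatment as answers, so minor medical events were expected to be entered.

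This reading is plausible and may well be what was meant. It does not rescue the sentence, which does not say it and uses a word that elsewhere in the section means data entry.

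A reader might also infer more than the text supports:

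- **That safety data will be captured selectively.** This follows only if staff apply 4b literally. The required question on the follow-up form and its prompt to complete the complications form carry no such filter and work against it. Nothing in the protocol shows that reporting of medical events differs by arm.
- **That no other route would catch these events.** This is not so. The follow-up question flags them, 4b itself lets through those that raise concern, and Section 4 has serious events presented to the co-investigators.
- **That 4b contradicts the sentence on serious adverse events.** The conflict is weak, because a serious event would plausibly count as a concern. The Section 3.2 that Section 4 cites for this does not exist in the current numbering, but that is a separate fault of cross-reference.

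**Conclusion.** Item 4b is wrong as written. Read literally, it contradicts the opening of Section 6.6, item 5c of Section 6.5 and the 2-week visit in Section 5.8. If it is followed literally, non-fatal medical events could be captured selectively, on an undefined judgement, in a trial where staff can see the treatment and which says it will compare complication rates.

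The point is a limited one. It rests on reading reporting as data entry, which is the usage of Section 6.6, and on staff giving 4b precedence over the unfiltered instructions, which is possible but not shown. The primary outcome and the listed secondary outcomes are not affected. The number of events at risk cannot be computed from the protocol. The correction is still worth making, because it is almost free and is sound whichever meaning was intended.

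**What to change.** Replace item 4b with: *All medical complications are recorded on this form; only those raising concern need in addition be sent to the review committee.*

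This agrees with the three recording instructions and keeps the limit on committee referral that 4b may have been meant to set. It changes no endpoint, no analysis and no clinical rule. The cost is one sentence in the manual and slightly more data entry. No new rule is needed for presenting particular classes of medical event, such as those with a hospital stay, to the co-investigators: the protocol does not equate hospitalization with a serious adverse event, and the contradiction can be removed without it.

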6.7 Follow-up Image Upload/Eval Form

The same procedure for baseline evaluation images will be used for follow-up evaluation images. Note that if a patient is reported to not be able to perform the squat and smile and/or heel lift test, a flag will appear and the option to upload an image will not be present.

Image Upload

Upload AP view:

 [Upload document](#)

Upload lateral view:

 [Upload document](#)

Upload squat and smile photo:

 [Upload document](#)

The squat and smile upload box will not appear here because the patient reported that they cannot perform the squat and smile test.

Upload heel lift photo here

 [Upload document](#)

The heel lift upload box will not appear here because the patient reported that they cannot perform the squat and smile test.

Check here for any extra images that need to be uploaded

- Extra Image #1
- Extra Image #2
- Extra Image #3
- Extra Image #4

1. The following questions are used for image evaluation

X Ray Evaluation

IM Nail breakage	 Yes  No	reset
IM Nail interlocking screw breakage	 None  1  2  3  4	reset
IM Nail interlocking screw loosening	 None  1  2  3  4	reset
Exfix schanz pin loosening	 None  1  2  3  4	reset
Exfix schanz pin breakage	 None  1  2  3  4	reset
Coronal plane angulation	 < 5 degrees  5-10 degrees  > 10 degrees  X-rays not adequate	reset
Coronal angulation (continuous)		"N/A" if x-rays not adequate
Coronal angulation direction	 Varus  Valgus  X-rays not adequate	reset
     Variable: fu_sagittal_angulation	 <5 degrees  5-10 degrees  >10 degrees  X-rays not adequate	reset
Sagittal plane angulation	 <5 degrees  5-10 degrees  >10 degrees  X-rays not adequate	reset
Sagittal angulation (continuous)		"N/A" if x-rays not adequate
Sagittal angulation direction	 Procurvatum  Recurvatum  X-rays not adequate	reset

2. The RUST Score questions will be used to evaluate quality of fracture healing

RUST Score	
Medial Cortex	 Fracture line, no callus  Fracture line, visible callus  No fracture line, bridging callus  X-rays not adequate
	reset
Lateral Cortex	 Fracture line, no callus  Fracture line, visible callus  No fracture line, bridging callus  X-rays not adequate
	reset
Anterior Cortex	 Fracture line, no callus  Fracture line, visible callus  No fracture line, bridging callus  X-rays not adequate
	reset
Posterior Cortex	 Fracture line, no callus  Fracture line, visible callus  No fracture line, bridging callus  X-rays not adequate
	reset
Squat and Smile Evaluation	
Squat and Smile	 Full squat without difficulty  Full squat with difficulty  Partial squat (< 90 degrees)  Unable to perform  Image not adequate
	reset

